### 6.3.5 Study Time Line (*provide diagram or table that outlines sequence/timing of study procedures*):

Assessment	Visit/follow-up interval relative to surgery								
	>1 month pre-op	<1 month pre-op	Day of surgery	Post-op day 1	Post-op week 3	Post-op week 6	Post-op month 3	Post-op month 6	Post-op year 1
Height/Weight	X	X	X	X	X	X	X	X	X
Pre-op bariatric work-up (counseling, labs, endoscopy, ultrasound, psychiatric evaluation)		X							
History and physical			X						
Schedule surgery			X						
Consent/Counseling on study			X						
Randomization			X						
Deidentification and population of secure data sheet			X	X	X	X	X	X	X
Pre-op labs (CBC, pregnancy test, renal panel, type and screen)			X						
Measure time for sleeve creation (sec)				X					
Measure total stapler loads fired				X					
Measure number of loads fired with technical difficulties				X					
Record staple line bleeding and hemostatic interventions				X					
Record time to load each staple cartridge				X					
Labs	X	X		X				X	X
Assess for adverse events				X	X	X	X	X	X

### 6.3.6 Dissemination plan to publish and/or present results of this research:

Data will be collected and interpreted with the goal of publication in a medical journal and presentation and national conferences

### 6.3.7 Has any other Scientific Review Committee/Organization reviewed this project for scientific merit? Yes [ ] No [x]. If yes, name the organization, year, and merit/score:

#### 6.4 Statistical Consideration.

##### 6.4.1 Statistical hypothesis, primary endpoints (i.e., primary outcome variables), and secondary endpoints, if any:

Research Hypothesis: As a superiority study, the research hypothesis is Ethicon linear cutting staplers with staple line reinforcement will have different outcomes when performing laparoscopic sleeve gastrectomy when compared to Covidien staplers with staple line reinforcement.

Primary objectives: Determine if using different brand staplers affects:

1. Time of creation of sleeve from first firing to completion
2. The percent of firings with technical difficulties
3. The time for tech to load each staple cartridge (aware of Hawthorne effect. Since both arms will be subject to Hawthorne effect, the only variable should be the stapler)

Secondary objectives: Determine if using different brand staplers affects:

1. Any bleeding after creation of the sleeve (annotating whether single or multiple interventions are required)
2. Weight loss
3. Leak rates

4. Hospital readmissions or emergency room visits (For complications including but not limited to dehydration, hemorrhage, leak, internal hernia, and pain; will annotate what complication warranted readmission)
5. Further sleeve interventions

#### **6.4.2 Data analysis:**

For the continuous primary endpoints, the two-sample t-test for 2 means will be used to compare the 2 Devices at Surgery. For the continuous secondary endpoints, such as weight loss, the General Linear Mixed Model Analysis for repeated measures over time will be used to test for the Device effect, Time effect and the Device by Time Interaction. For the binary secondary endpoints (Yes/No), such as Staple line leak, Readmission or ER visits, further sleeve interventions, over time, the General Estimating Equations (GEE) analyses will be used to test for Device effect, Time effect and the Device by Time Interaction. For all tests, the level of significance is set at 0.05.

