## **2.4 Methodology / Technical Approach (including the number of subjects/records to be studied):**

New bariatric patients who have elected for a sleeve gastrectomy as part of standard of care will be invited to participate in the study during the bariatric clinic at William Beaumont Army Medical Center. Patients who meet the inclusion criteria will be invited to participate in the study. Please see Section 6.2.3 for specific details on study recruitment and Section 6.2.4 for specific details on the consent process. These patients will be consented in the bariatric clinic by a research resident listed on the protocol.

Three folders will be made, one for each bariatric surgeon, and 25 Covidien cards and 25 Ethicon cards will be placed into each for a total of 150 patients. All bariatric surgeons are trained and familiar with both devices. Once consented, a card will be removed at random to determine which stapler will be used. Bioabsorbable staple line reinforcement will be utilized with both staplers. Once in the operating room, the case start time, time from first staple firing to completion of sleeve, total stapler loads required, number of staple misfires, character of any staple line bleeding, and time for tech to load each cartridge will be recorded on a data collection sheet by a research resident, listed as an associative investigator on this protocol. The subject's post-operative course will follow the bariatric protocol. During follow-up, they will be monitored for weight loss, post-operative complications, and any other required interventions. This information will be obtained by reviewing the subject's medical record after follow-up appointments. Per the bariatric protocol, subjects will follow-up as noted in 6.3.5. If a patient withdraws consent for the study prior to surgery, they will still receive surgery and perioperative treatment in line with institutional protocol, and they will be withdrawn and create a vacancy for a new subject. If a patient withdraws consent after surgery, we will cease logging data for the study on that subject. We will clarify whether they want all data to be removed from the study or if they simply want no more data to be entered into the study and abide by their wishes, and they will remain in the original randomized group in accordance with intention-to-treat principles.

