**6.3.2 Study Methodology/Procedures:**

Patients who express an interest in bariatric surgery will attend a bariatric seminar and initiate the process of scheduling bariatric surgery per department protocol. Once qualified for surgery, the patients will present to bariatric clinic, which takes place in the general surgery clinic on Tuesdays, and have a one-on-one discussion about their desired surgery with a staff physician. If the patient desires a sleeve gastrectomy, the study will be discussed. Consent will be obtained, and the patient will be randomized into the Covidien or Ethicon group. The subject will proceed with surgery per department protocol. In the operating room, a data collection sheet will be available in the operating room to make note of time for creation of sleeve from first firing to completion, total number of staple loads fired, number of misfires, character of any bleeding at the staple line and which interventions were required to control it, and time it takes for the surgical technologist to reload the stapler. At William Beaumont surgical technologists are trained on loading each linear cutting stapler by the Covidien and Ethicon representatives. We will still ensure at the start of the case they are familiar with loading the provided device. No additional training for device will be mandated, as surgical technologist turnover would make this difficult to provide equal training, and it would detract from internal and external validity, since we do not normally provide extra training. Typically the sleeve is created by staff or higher level residents (PGY-2 and above). However, all residents are trained on the devices and are therefore capable of creating the sleeve with close staff supervision, as is standard for our institution. For the purpose of this study, we intend on maintaining this practice since all level residents may be assisting and performing this surgery throughout their residency and deviation would lead to questionable internal validity. After surgery, patients will be admitted to the hospital, and care will follow the department's bariatric protocol. Once discharged, they will follow-up at 3 weeks, 6 weeks, 3 months, 6

months, and then annually. Subjects will be followed for 1 year after surgery. During that time, weight loss, presence of staple line leaks, any readmissions, and any other interventions will be monitored.

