### **6.3.4 Data Collection (*all study variables/instruments/questionnaires to be administered*):**

There will be two separate data logs maintained for the purposes of this study. The first log (master key) will contain all subject identifiers and PHI. Specifically, the master key will include:

- Patient identifier (to be linked to study log)
- Patient name
- Date of birth
- Surgeon
- Date of operation
- Family member prefix with last four digits of the social security number

The second log (data collection sheet) will include patient identifier to link to master key, but include no other PHI or direct identifiers. A data collection sheet that omits identifiable patient health information (only a pre-assigned identifier unique to the study) will be present in the operating room. This information will be transcribed to a data log on a secure computer. Specifically, the data collection sheet will include;

- Patient identifier (to link to master key)
- Gender
- Race
- Age
- Pre-operative height (needed to calculate ideal body weight)
- Pre-operative weight
- Intra-operative data points, to include time to load stapler, time to create sleeve, intra-operative bleeding or leak, and number of staple load misfires
- Weight recordings from follow-up appointments
- Annotations of any re-admissions or complications after surgery
- Follow-up weight (at follow up points)
- Weight loss (at follow up points)
- Need for hospital readmission or emergency room visits with annotation of the complication that caused the increased need for hospital care

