A research resident listed on the protocol will be present during the operation to populate the data points on the data collection sheet. Timing, done by a physician, will require a stopwatch to monitor the total sleeve creation time and the time it takes to load each stapler cartridge. This data will be transcribed into the Excel data collection spreadsheet on a secure, password-protected computer. Data from follow-up visits, such as complications and weight, will be acquired via chart review through AHLTA and CHCS. The master key with patient identifiers will be linked to the data log sheet to allow physician researchers to acquire this information from the electronic medical records. All information will remain on a secure hospital computer and will be intermittently updated by a research resident as the study progresses. As listed above, information acquired from chart review during this study will include: follow-up weight, weight loss, and need for hospital readmission or emergency room visits with annotation of the complication that caused the increased need for hospital care. Other information, such as name, height, race, age, family member prefix with last four digits of the social security number, initial weight, surgeon, date of the operation, data points collected in the operating room (time to load stapler, time to create sleeve, intra-operative bleeding or leak, and number of staple load misfires) will

have already been added to the list shortly after the patient's procedure.

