#### **6.4.3 Sample Size Estimation:**

75 in each arm for a total of 150 patients. The preliminary power analysis indicated 64 in each arm to be sufficient, to be able to detect a medium effect size of 0.5 for the two-sided t-test, with  $\alpha = 0.05$  and 80% power, so 11 extra patients per arm have been added for attrition. The power analysis was based on the research hypothesis of a difference in the 2 devices, with this superiority study using time to create sleeve as the primary variable.

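### Allocation is stratified by surgeon, but sleeve-creation time is compared with an unadjusted t-test; a surgeon term would add precision at almost no cost if surgeons differ

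*Combined protocol and SAP*

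**What the plan says.** - **Allocation (section 2.4).** "Three folders will be made, one for each bariatric surgeon, and 25 Covidien cards and 25 Ethicon cards will be placed into each", giving 150 patients. The draw is described as: "Once consented, a card will be removed at random to determine which stapler will be used". Device is therefore balanced 25:25 within each surgeon once a folder is used up. Section 6.3.1 mentions only shuffled cards, which is compatible with this.
- **Primary variable (section 6.4.3).** The power analysis was done "with this superiority study using time to create sleeve as the primary variable".
- **Analysis (section 6.4.2).** "For the continuous primary endpoints, the two-sample t-test for 2 means will be used to compare the 2 Devices at Surgery". Section 6.4 contains no surgeon, stratum or covariate term.
- **Operator (section 6.3.2).** The folder surgeon need not make the sleeve: "all residents are trained on the devices and are therefore capable of creating the sleeve with close staff supervision".
- **Withdrawal before surgery (section 2.4).** Such patients are replaced: "they will be withdrawn and create a vacancy for a new subject".
- **Recording of surgeon (section 6.3.4).** Surgeon is an item in the master key ("The first log (master key) will contain all subject identifiers and PHI") and appears again in the list of recorded items: "initial weight, surgeon, date of the operation, data points collected in the operating room". It is not among the items of the de-identified data collection sheet.

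**The concern.** Stratifying by surgeon removes differences between surgeons from the device comparison. A t-test that ignores the strata does not use this. Its standard error still includes the between-surgeon variance, although the estimated device difference no longer varies because of it. The reported standard error is then too large, the confidence interval is wider than the design warrants, and the test rejects less often than 5% under the null.

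Precision has a practical consequence in this trial. The abstract (section 2) says that if neither device proves superior, cost may decide which is used. A null result therefore leads to a decision, and the width of the interval tells a reader which differences that null result excludes.

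The point covers sleeve-creation time only. It makes no claim about cartridge loading time, the percent of firings with technical difficulties, weight loss or the binary GEE models.

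**Working it through.** **Inputs from the documents.** Standardised effect d = 0.5, two-sided α = 0.05, 80% power, 64 per arm raised to 75 (section 6.4.3); three folders of 25 + 25 (section 2.4). Sleeve time is measured at surgery and patients who withdraw beforehand are replaced, so about 75 per arm is the relevant size.

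**Input not in the documents.** The share r of sleeve-time variance due to surgeon is assumed at 0, 5, 10, 20 and 30%. With three equally spaced surgeon means, the gap between fastest and slowest is 2√(1.5r) total SDs, or about 0.5, 0.8, 1.1 and 1.3 SDs for the non-zero shares.

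**Step 1: the plan's own figure.** The noncentral t with noncentrality d√(n/2) and 2n − 2 degrees of freedom gives power 0.795 at 63 per arm and 0.801 at 64. The stated 64 per arm is reproduced. At 75 per arm the power is 0.8604.

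**Step 2: cost of the surgeon term.** Two degrees of freedom. At r = 0, power goes from 86.04% (148 df) to 86.03% (146 df) at 75 per arm, and from 80.15% (126 df) to 80.14% (124 df) at 64 per arm. The critical t at 75 per arm moves from 1.9761 to 1.9763.

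**Step 3: gain if surgeons differ.** One normal outcome per patient, additive surgeon effects with variance r, residual variance 1 − r, and full 25:25 balance.

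- Adjusted power: noncentral t with effect 0.5/√(1 − r) and 146 df. At r = 0.20 the effect is 0.5/√0.80 = 0.559 and the noncentrality 0.559 × √37.5 = 3.42, giving power 0.925.
- Interval: the t-test's expected variance is (1 − r) + r × 75/74, against 1 − r after adjustment. At r = 0.20 the width ratio is √(0.80/1.0027) = 0.893, that is 10.7% narrower.
- t-test type I error and power: simulation, 200,000 replicates.

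| Surgeon share r | t-test type I error | t-test power | Adjusted power | Interval narrower by |
|---|---|---|---|---|
| 0% | 5.0% | 86.0% | 86.0% | 0% |
| 5% | 4.4% | 86.7% | 87.7% | 2.6% |
| 10% | 3.9% | 87.3% | 89.4% | 5.2% |
| 20% | 2.8% | 88.6% | 92.5% | 10.7% |
| 30% | 1.9% | 90.1% | 95.3% | 16.5% |

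The adjusted test stays near 5% throughout.

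**Step 4: dilution by other operators.** Suppose a case carries its folder surgeon's effect with probability f and otherwise an effect drawn at random from the same three values. The folder then explains about f² × r of the variance; for r = 0.20 and f = 0.75 that is 0.5625 × 0.20 = 0.1125. Both r and f are assumed (simulation, 50,000 replicates).

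| f | Narrower, r = 10% | Narrower, r = 20% | Power at r = 20%, t-test v adjusted |
|---|---|---|---|
| 75% | 2.9% | 5.8% | 87.3 v 89.8% |
| 50% | 1.3% | 2.6% | 86.8 v 87.8% |
| 25% | 0.3% | 0.6% | 86.2 v 86.5% |

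**Step 5: folders not used up.** With only 25 of 50 cards drawn from each folder (20,000 replicates), the t-test's type I error is about 4.5, 3.9 and 3.3% at r = 10, 20 and 30%, closer to nominal than with full folders. At r = 20% the power is 56.6% for the t-test and 65.7% adjusted, a larger gain than with full folders.

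**The case against.** The t-test is a valid analysis, its error is on the conservative side, and the sample size matches it. Nothing in the plan contradicts itself, so this is a choice between two valid analyses. That stands, and it limits the weight of the point.

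The gain also rests on an assumed surgeon share. The plan gives no SD for sleeve time and no difference between surgeons, and says that all of them are trained on both devices. Nor does it show that they are alike: section 2.4.1 leaves the choice of later loads partly to the surgeon, and those loads are fired inside the timed interval. The size of the gain is therefore unknown, and it could be close to nil.

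Residents may make the sleeve, so the folder surgeon is a partial stand-in for the operator. This also stands, and the diluted figures in Step 4 may be nearer the truth than those in Step 3, although a supervising surgeon may still influence the time.

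The type I error figures in Step 3 assume full folders. Section 6.4.4 allows early stopping, and the dates in section 10 (31 August 2016 to 31 March 2018, 19 months including analysis), less one year of follow-up, leave about 7 months to enrol 150 patients. Partly used folders soften those figures but increase the power gain from adjusting, so they do not weaken the recommendation.

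Finally, surgeon is listed in the master key and not on the de-identified sheet. A surgeon code has to be carried into the analysis file, which is a small step.

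**Conclusion.** The concern holds as a point of efficiency, not validity. The design stratifies by surgeon and the analysis of the variable that sized the trial ignores it. With full folders and the folder surgeon's effect present in every case, assumed shares of 5 to 30% mean an interval 2.6 to 16.5% narrower and about 1 to 5 more points of power. Dilution by other operators brings this down to between 0.3 and 5.8% narrower at shares of 10 to 20%. If surgeons do not differ there is no gain and the cost is about 0.01 points of power. Confidence in the size is only moderate, because neither the surgeon share nor the mix of operators is given. The change is worth making because the possible loss is negligible under every assumption tried.

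**What to change.** In section 6.4.2, replace the t-test for sleeve-creation time with, for example: *Sleeve-creation time will be compared between devices with a linear model including device and surgeon (three levels, the randomisation folder) as fixed effects; the adjusted device difference will be reported with its 95% confidence interval.* The unadjusted t-test can be kept as a sensitivity analysis. The term should be fixed before outcome data are examined, so that it cannot appear to be chosen on the results.

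In section 6.3.4, state that a coded surgeon field is carried from the master key into the analysis file and that it identifies the randomisation folder, in case an operation passes to another surgeon.

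The cost is a sentence or two and two degrees of freedom, with no extra patients or measurements. The sample size and the other analyses are unaffected by this point.

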comorbidities (hypertension, obstructive sleep apnea, pseudotumor cerebri, hyperlipidemia, diabetes, etc). All patients undergo psychiatric screening, laboratory assessment to rule out other cause of obesity, such as hypothyroidism, esophagogastroduodenoscopy, ultrasound of their gallbladder, and multiple counseling sessions prior to scheduling surgery. Patients may choose which bariatric procedure they prefer between sleeve gastrectomy, roux-en-y gastric bypass, and gastric band placement. Once scheduled for surgery, they will present to the hospital 6th floor. They will be given one dose of 5000 units subcutaneous heparin. Preoperative antibiotics of cefazolin or clindamycin will be administered within 30 minutes of surgery start time. Patients will be placed on the operating table in the supine position with a footboard in place. Sequential compression devices will be placed on the lower extremities. General endotracheal anesthesia will be induced. The abdomen will be prepped and draped in the usual sterile fashion. A time out will be completed, verifying the correct patient, procedure, site, positioning, and special equipment prior to starting the surgery. A fenestrated bougie will be placed through the patient's mouth, into the stomach. Pneumoperitoneum will be obtained, and a trocar with a laparoscope will be inserted. The abdominal contents will be inspected for evidence of injury. Three additional trocars will be placed under direct visualization and a Nathanson retractor will be used to retract the liver. Negative pressure will be applied to the fenestrated bougie after proper positioning laparoscopically. The stomach will be inspected, and a site 4-6 cm proximal to the pylorus will be identified. A defect will be made in the greater omentum at this site close to the greater curvature of the stomach using a harmonic scalpel. Dissection will be carried along the greater curvature of the stomach to the gastroesophageal junction, taking care not to injure the spleen. Starting with a black load with and absorbable polymer membrane reinforcement on either the Covidien iDrive with reinforced Tristaple technology or the Ethicon Echilon powered stapling device with Gore Seamguard reinforcement. Typically at our institution, the Ethicon Echilon device is used more frequently simply due to availability, but all bariatric surgeons are trained on both devices. Subsequent stapler loads will be surgeon and patient-dependent. Typically Ethicon black loads will be used until the fundus of the stomach, at which point a blue load without reinforcement is used. For Covidien, the black load is typically exchanged for a purple load near the fundus. Once the sleeve is complete, the stomach will be submerged in saline, and the remnant stomach will be insufflated, looking for any evidence of air leak, which would be repaired prior to conclusion of the case. The staple line will be inspected for bleeding. The gastric remnant will be removed though a port, and the abdomen will be desufflated. Incisions will be closed with 4-0 monocryl and covered in Dermabond. Patients are kept NPO and monitored overnight with intravenous fluids. They are started on water sips the next morning and are advanced to a bariatric liquid diet if they tolerated water sips. If they have adequate pain and nausea control and are taking in adequate fluid, they are discharged home on post-operative day one. They will follow-up at week 3, week 6, month 3, month 6, and annually.

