**3. OBJECTIVES AND SPECIFIC AIMS:**

Primary objectives: Determine if using different brand staplers affects:

1. Time of creation of sleeve from first firing to completion
2. The percent of firings with technical difficulties
3. The time for tech to load each staple cartridge (aware of Hawthorne effect. Since both arms will be subject to Hawthorne effect, the only variable should be the stapler)

Secondary objectives: Determine if using different brand staplers affects:

1. Any bleeding after creation of the sleeve (annotating whether single or multiple interventions are required)
2. Weight loss
3. Leak rates
4. Hospital readmissions or emergency room visits (For complications including but not limited to dehydration, hemorrhage, leak, internal hernia, and pain; will annotate what complication warranted readmission)
5. Further sleeve interventions

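### Cartridge load time and percent of difficult firings are repeated within a patient, but section 6.4.2 gives primary endpoints only an independent two-sample t-test and names no unit of analysis

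*Combined protocol and SAP*

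**What the plan says.** Sections 3 and 6.4.1 list the same three primary objectives. The first, "Time of creation of sleeve from first firing to completion", gives one value per patient. The other two do not: "The percent of firings with technical difficulties" and "The time for tech to load each staple cartridge".

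The data are collected at the finer level. Under section 6.3.4 a physician times by stopwatch "the time it takes to load each stapler cartridge", and the timeline in 6.3.5 repeats this for every cartridge. Section 6.3.2 has the operating-room sheet record "total number of staple loads fired, number of misfires". Section 2.4.1 adds: "Subsequent stapler loads will be surgeon and patient-dependent". Since total loads are recorded case by case, the number evidently is not fixed.

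For analysis, section 6.4.2 says: "For the continuous primary endpoints, the two-sample t-test for 2 means will be used to compare the 2 Devices at Surgery". Methods for correlated data appear only for secondary endpoints, and only over follow-up: "For the continuous secondary endpoints, such as weight loss, the General Linear Mixed Model Analysis for repeated measures over time will be used", with GEE for the binary secondary endpoints. Every test is at 0.05.

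Section 6.4.3 sizes the trial in patients (64 per arm, 75 with attrition) on sleeve creation time alone.

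**The concern.** A two-sample t-test assumes independent observations. Cartridge times from one operation share a patient, a surgeon and a theatre team, so they are likely to be correlated. Firings within one patient share tissue and operator in the same way. An analyst who opens the spreadsheet, finds one load time per cartridge and runs the t-test on all of them would be following section 6.4.2 to the letter. The interval would be too narrow and the error rate above the stated 0.05.

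The unit also changes what is estimated. If the number of loads varies, a cartridge-level mean weights patients by how many loads they needed; a mean of patient means does not.

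For the percent of firings, the plan does not say whether the percent is computed per patient and treated as continuous, which would bring it under the t-test, or computed once over all firings in an arm, for which no test is named.

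Load time matters here because it is one of the two outcomes in the hypothesis that closes section 5.1. Leaving the unit open allows it to be chosen after the data are seen.

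**Working it through.** **Plan's own figure.** Inputs from 6.4.3: standardised difference 0.5, two-sided alpha 0.05, power 80%.

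- Normal approximation: n = 2(1.960 + 0.842)² / 0.5² = 62.8, so 63 per arm.
- Noncentral t: 63.77, so 64 per arm, as stated. Power at 64 is 80.1%.
- 64 + 11 = 75 per arm, which allows for 11/75 = 14.7% attrition.

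These figures reproduce and are not in dispute.

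**Assumed inputs.** The documents give no number of loads per patient (m), no within-patient correlation (ICC) and no difficulty rate. All three are varied below.

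**Load time, t-test on every cartridge.** Design effect DE = 1 + (m − 1) × ICC. True two-sided alpha = 2 × [1 − Φ(1.96/√DE)]. With m = 6:

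| ICC | DE | 1.96/√DE | True alpha |
|---|---|---|---|
| 0.1 | 1.5 | 1.600 | 11.0% |
| 0.2 | 2.0 | 1.386 | 16.6% |
| 0.4 | 3.0 | 1.132 | 25.8% |
| 0.6 | 4.0 | 0.980 | 32.7% |

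Over m = 4 to 8 and ICC 0.05 to 0.5, the range is 6.8% (m = 4, ICC 0.05) to 35.6% (m = 8, ICC 0.5).

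**Simulation check.** 75 patients per arm, m = 6, no device effect, 10,000 runs:

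| ICC | All cartridges | One mean per patient |
|---|---|---|
| 0.1 | 10.8% | 5.0% |
| 0.3 | 21.5% | 5.2% |
| 0.5 | 28.7% | 4.8% |

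The simulation error at 5% is √(0.05 × 0.95/10,000) = 0.2 percentage points, so the last column is consistent with 5%.

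**Percent of firings.** Beta-binomial simulation, 75 per arm, 4 to 8 firings per patient, no device effect, 10,000 runs. Ranges are over difficulty rates of 1%, 2%, 5% and 10%:

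| ICC | Pooled firings, z-test | t-test on per-patient percent |
|---|---|---|
| 0 | 4.6% to 5.2% | 5.0% to 5.3% |
| 0.1 | 10.7% to 11.7% | 3.9% to 5.1% |
| 0.3 | 22.1% to 22.9% | 2.4% to 5.2% |

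The values below 4% in the last column occur only at a 1% difficulty rate. A separate simulation (6 firings, rates 2% to 5%, ICC 0.05 to 0.3, 8,000 runs) gave 7.5% to 21.7% for pooled firings and 4.1% to 5.0% for the per-patient percent.

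Between 54% and 97% of patients had no difficult firing in the first set of scenarios. The per-patient percent is therefore discrete with many zeros, yet the t-test on it does not exceed its nominal level by more than about 0.3 points in any scenario.

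**The case against.** The strongest reply is that the plan never says it will analyse cartridges or pool firings. The word each describes what is measured, not the unit of analysis, and the context points to the patient: patients are randomised, the data sheet in 6.3.4 is kept by patient identifier, and the t-test is sized in patients. Section 6.4.2 refers to continuous primary endpoints in the plural and names no binary one, so a per-patient percent fits the t-test naturally. On that reading the planned test holds its level for both endpoints.

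Much of this stands. The plan does not commit to a cartridge-level or pooled analysis, so the inflation is conditional on that choice. A reader might infer that the percent endpoint has no valid test at all. The documents do not support that: computed per patient, it can be read as continuous, and the t-test on it is close to nominal or conservative.

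A reader might also infer that load time decides which stapler is preferred. The abstract ties preference to clinical outcomes, with cost as the fallback, so this too goes beyond the text.

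The reply does not close the gap. No section states the patient-level reading. The endpoint is worded per cartridge, and the methods that would handle repeated values are reserved for other endpoints.

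**Conclusion.** The point holds as an unspecified unit of analysis for two of the three primary endpoints, with a material consequence if the wrong unit is used. For load time, a cartridge-level t-test has a true type I error of about 11% to 33% at an assumed 6 loads and ICC 0.1 to 0.6. For difficult firings, pooling gives about 7.5% to 23% at assumed ICC 0.05 to 0.3. With one value per patient, both endpoints hold about 5%; the percent endpoint is conservative at worst, at a 1% difficulty rate.

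The direction is certain for any positive within-patient correlation. The size depends on inputs that the documents do not give.

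The sample size is not affected. Sleeve creation time has one value per patient, so nothing here changes the 64 or 75 per arm. The change should be made before the data are analysed.

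**What to change.** In section 6.4.2, name the patient as the unit of analysis and define one value per patient: mean load time over that patient's cartridges, and difficult firings divided by total firings. Compare devices on these values in a linear model with device and surgeon. Surgeon belongs in the model because section 2.4 randomises from a separate folder for each of the three surgeons.

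An equally good alternative keeps the finer data:

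- **Load time:** a linear mixed model with device and surgeon as fixed effects and a patient random effect.
- **Difficult firings:** a logistic model of events out of firings, clustered on patient (for example GEE with a small-sample correction), with surgeon as a factor. If events are sparse, a permutation test of the per-patient percent stratified by surgeon is a workable fallback.

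Choose one approach in advance. A technologist random effect is optional, because section 6.3.4 does not list technologist identity; it would need one extra field on the data sheet.

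The cost is a few sentences in the analysis section. The load times and firing counts are already to be collected, and no extra patients are needed. Intervals will be wider than those from a cartridge-level or pooled analysis, which would overstate the precision.
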